16. SUPPLEMENTAL MATERIALS..... 35

LIST OF ABBREVIATIONS

AE	Adverse Event
CRF	Case Report Form
CT	Computed Tomography
CFR	Code of Federal Regulation
pCR	complete pathologic response
FDA	Food and Drug Administration
FTV	Functional Tumor Volume
HIPAA	Health Insurance Portability and Accountability Act
IFU	Indication for Use
IRB	Institutional Review Board
MHS	Memorial Healthcare System
MR	Magnetic Resonance
NACT	Neoadjuvant Chemotherapy
NAT	Neoadjuvant Treatment
NSR	Nonsignificant Risk
OHR	Office of Human Research
PHI	Protected Health Information
PI	Principal Investigator
RCB	Residual Cancer Burden
RFS	Recurrence Free Survival
SAE	Serious Adverse Event
SCOUT	SAVI SCOUT Device (Cianna Medical, Inc.)
UADE	Unanticipated Adverse Device Event

PROTOCOL SUMMARY

Title: Evaluation of longer duration use of the SAVI SCOUT Surgical Guidance System for Excision of Breast and Axillary Lesions in Neo-adjuvant Therapy Patients: A Pilot Study

Purpose: The purpose of this study is to evaluate the performance of FDA cleared SAVI SCOUT Breast Localization and Surgical Guidance System (SCOUT) over a longer duration prior to surgery. The device(s) is a non-wire system, which uses nonradioactive light-activated radar, to provide breast surgeons with real-time guidance to locate and remove the target lesion(s) in the breast and/or axillary tissue.

The SCOUT device standard of care use is placement up to 365 days prior to surgery to assist surgeons in the localization and retrieval of breast/axillary lesions. Routine image-guided methods (Mammography, Ultrasound, and CT) are used. In this study, we will assess the longer term placement of 1 – 4 SCOUT devices over an extended time (31 - 365 days) in order to address the needs of patients who require neoadjuvant treatment prior to definitive surgery.

Hypothesis: Placement of the SCOUT device(s) prior to neoadjuvant treatment with biologic (hormonal) and/or chemotherapy allows for long-term localization of breast/axillary lesions targeted for surgical excision.

Objectives: Main Objective: To show that the SCOUT device(s) can be used over an extended time (up to 365 days) prior to surgery to successfully guide surgical excision of breast or axillary lesions in patients who undergo neoadjuvant therapy.

Primary Endpoint:

The primary endpoint of this study is successful surgery. Successful surgery (defined as one where the device stays in place and can be removed successfully during surgery) when this device(s) is placed 31 - 365 days prior to surgery. Unsuccessful surgery is defined as one where the device(s) does not stay in place and/or cannot be removed successfully during surgery) when this device(s) is placed 31 - 365 days prior to surgery.

Secondary Endpoints:

- Number of days prior to surgery (31 - 365) that the SCOUT device(s) is placed by the radiologist to localize the target breast / axillary tissue.
- Success rate of device(s) placement by radiologist (within 1 cm of the center of the target tissue).
- Success rate of SCOUT localization procedure(s) stability. The SCOUT(s) should

not migrate more than 5 mm between day 0 - 365 days pre-surgery. This is measured on routine mammogram and/or ultrasound.

- Rate of device-related complications.
- The number of additional localization procedures needed to supplement the initial SCOUT(s) standard of care localization procedure(s).

Population: The study population consists of 25 - 35 adult surgical patient volunteers who plan to have definitive breast cancer surgery at Memorial Healthcare System (MHS) Hospitals after neoadjuvant treatment.

Phase: N/A

Number of Sites: 3, listed below:

1. Memorial Regional Hospital
[name]
[name]
2. Memorial Hospital West
[name]
[name]
3. Memorial Hospital Miramar
[name]
[name]

Description of Intervention: Using Radiology standard of care imaging guidance, (Mammography, Ultrasound or CT) the SCOUT device(s) will be placed percutaneously 31 - 365 days prior to the scheduled surgical excisional procedure(s).

During the surgical procedure, the SCOUT system will be used to locate and excise the device and target tissue.

Study Duration: Approximately 25 months. Accrual of 25 - 35 patients (total) from MHS will occur within 12 months. Final data analysis will be completed within 1 month after the last patient is treated. Interim subject accrual will be evaluated after 3, 6, 9 months.

Subject Participation Duration: 1 month – 13 months.

Estimated Time to Complete Enrollment: 6 – 12 months.

Schematic of Study Design:

Patient has SAVI SCOUT LOCALIZATION by Radiologist at any time prior to neoadjuvant treatment
*SAVI SCOUT placed anytime **FDA clearance 10/31/17***

Research Surgeon/MCI Research Nurse/ Investigator

Study Visit 1

ELIGIBILITY
and
CONSENT and
ENROLLMENT

Subject meets Inclusion/Exclusion Eligibility
Informed Consent: Before or after SAVI SCOUT LOCALIZATION and PRIOR TO NACT
Documentation of Consenting Process Form

Research Radiologist

Completes Device Placement Form
Assigns Study ID
Copy of Consent and Study ID sent to OHR for tracking.

Sometimes, additional studies ordered by Med-Onc can impact surgical plan.

Neoadjuvant treatment begins.

**Breast Radiologist performs standard of care pre-operative skin marking*

Study Visit 2
(Day up to 30
prior to surgery)

Research Radiologist

Completes Device Placement Recheck [Device Placement Form] on standard of care imaging and performs audio verification and repeat skin marking if requested as standard of care by surgeon.

Research Surgeon

Excision (standard of care) performed by Research Surgeon
Device Surgical Excision Form

Study Visit 3
(Day of surgery
+ 30 days)

Research Radiologist completes:

Study Completion Form
ALL Unanticipated Adverse Device Events (UADE) Form

**Note distinction of Breast Radiologist (standard of care SCOUT) vs. Research Radiologist (who Completes Forms)*

1. KEY ROLES and contact information:

Principal Investigator:

[name].
Chief, Women's Imaging Center
Radiology Associates of Hollywood, Inc.
Memorial Regional Hospital
[name]
[name]

[contact]
[contact]

Institutions:

Memorial Healthcare System Women's Imaging Centers:

Memorial Regional Hospital
[name]
[name]

Memorial Hospital West
[name]
[name]

Memorial Hospital Miramar
[name]
[name]

Key Personnel: **Data Manager:** [name].

2. BACKGROUND INFORMATION AND SCIENTIFIC RATIONALE:

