In the event that the SCOUT device is not detected over 31 - 365 days, we have an existing standard of care safety net procedure to use an additional localization device at no charge to the patient (via a second SCOUT device placement and/or standard wire localization).

Patients will be scheduled for their standard of care preoperative imaging 0 – 30 days prior to the scheduled surgery for the radiologists to perform skin marking (standard of care). At that visit, the radiologists will use the SCOUT system to verify that the SCOUT device(s) is detectable from the skin. If the radiologist cannot detect the device(s) at the target, this will be immediately communicated to the surgeon who will determine whether to request an additional SCOUT device(s) or standard wire localization *at no additional cost* to the patient. Although the patient will end up with the standard of care procedure, a slight increased procedure time might occur since the first SCOUT device(s) will need to be removed in addition to the subsequent localization device. We anticipate this risk to be less than 1% (1/150 patients), which is less than routine standard of care (2 - 3%) pre-operative wire localization migration. Vasovagal risks that occur with standard of care pre-operative wire localizations (2 - 3%) have not occurred in our 150 patient experience with SAVI SCOUT. Subjects will be instructed to contact the study investigators about device-related issues. These issues will be promptly communicated to the study investigators for reporting as needed.

2.3.4 *Justification for Conducting the Study*

Risks to the subjects associated with this study are low. SAVI SCOUT is used routinely by the surgeons participating in this study in this population. The vast majority of these subjects would receive one or more SAVI SCOUT device(s) prior to surgery. The overall increase in risks to the subjects is small and they may benefit from the improved accuracy of identifying the target lesion(s) for surgical excision. This benefit is anticipated to exceed the rare potential instances of device migration or inability to locate the device(s).

In order to protect the privacy of study participants, all study data will be restricted to password protected computers and servers on the protected MHS and Envision Physician Services (formerly Sheridan) networks. Any study data will be de-identified before being sent to a third party.

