4.1 Study Outcome Measures

4.1.1 Primary Endpoint:

The primary endpoint of this study is successful surgery. Successful surgery (defined as one where the device(s) stays in place and can be removed successfully during surgery) when this device(s) is placed 31 - 365 days prior to surgery. Unsuccessful surgery is defined as one where the device(s) does not stay in place and/or cannot be removed successfully during surgery) when this device is placed 31 - 365 days prior to surgery.

4.1.2 Secondary Endpoints:

- Number of days prior to surgery (31 - 365) that the SCOUT device(s) is placed by the radiologist to localize the target breast / axillary tissue.
- Success rate of device(s) placement by radiologist (within 1 cm of the center of the target tissue).
- Success rate of SCOUT localization procedure(s) stability. The SCOUT should not migrate more than 5 mm between day 0 - 365 days pre-surgery. This is measured on routine mammogram and/or ultrasound.
- Rate of device(s) related complications.

5. STUDY ENROLLMENT AND WITHDRAWAL:

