9.2 Final Analysis Plan

Simple statistics will be used to evaluate the collected data as to the data elements listed in the primary and secondary endpoints.

10. SOURCE DOCUMENTS AND ACCESS to SOURCE DATA/DOCUMENTS:

MHS and Envision Physician Scientific Research (formerly Sheridan Scientific Intelligence) will maintain appropriate medical and research records for this study, in compliance with ICH E6, Section 4.9 and regulatory and institutional requirements for the protection of confidentiality of subjects.

The main source of data will be the electronic and/or physical medical records of our institution. In addition to basic demographic information, notes from the appropriate radiologic, surgical and pathology procedures will be accessed in order to complete the case report forms.

Note that the forms must be completed at the time of the relevant procedure by the study coordinator and/or investigator, since these data might not be captured in the standard reports.

Patient Inclusion/Exclusion Eligibility Enrollment Form
Device Placement Form
Device Excision Form
Unanticipated Adverse Device Event(s) Form(s)
Study Completion Form

De-identified (identified by study ID number only) copies of all medical images depicting the breast lesion and SCOUT device may be shared for scientific presentations. These images are necessary for complete analysis of the reasons if there is any possible failure of the detection of FDA cleared SCOUT system over a longer duration prior to breast and/or axillary lymph node surgery. These images include the following:

1. Diagnostic imaging
2. Image-guided device placement
3. Imaging of device verification (if available)
4. Additional localization imaging (if necessary)
5. Post-excision specimen radiograph

All DICOM images should be de-identified according to the guidelines specified by the NCI Cancer Imaging Archive. For details, see:

<https://wiki.cancerimagingarchive.net/display/Public/De-identification+Knowledge+Base>

11. ETHICS AND PROTECTION OF HUMAN SUBJECTS:

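### Section 4.1.2 drops the Summary's count of additional localizations and, separately, the primary definition lets an unmoved, undetected device removed with a second localization count as a success

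*Combined protocol and SAP*

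**What the plan says.** **Secondary endpoints.** The Protocol Summary gives five. The fifth is "The number of additional localization procedures needed to supplement the initial SCOUT(s) standard of care localization procedure(s". Section 4.1.2 repeats the first four and stops at "Rate of device(s) related complications". Neither place says which list takes precedence.

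**Primary endpoint.** The Summary and Section 4.1.1 use essentially the same wording. A successful surgery is "defined as one where the device(s) stays in place and can be removed successfully during surgery". The converse is also given: "Unsuccessful surgery is defined as one where the device(s) does not stay in place and/or cannot be removed successfully during surgery". Neither sentence mentions whether the device was detectable or whether another localization was used.

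**Additional localization.** Section 2.3.3 plans for a device that is not detected: "we have an existing standard of care safety net procedure to use an additional localization device at no charge to the patient". It continues: "If the radiologist cannot detect the device(s) at the target, this will be immediately communicated to the surgeon", and the surgeon then decides whether to ask for a second SCOUT or a wire. The first device still has to come out at surgery. Section 6.2.1 adds a second trigger, a position not verified to within 5 mm of the initial placement. Section 2.3.3 puts the anticipated risk below 1% (1/150 patients).

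**Analysis.** On how the endpoints will be analysed, Section 9.2 says only this: "Simple statistics will be used to evaluate the collected data as to the data elements listed in the primary and secondary endpoints".

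**The concern.** The main objective is that a device left in for up to 365 days can guide the excision. Sections 2.2 and 2.3.2 present fewer pre-operative procedures as the expected gain. The count of additional localizations is the only endpoint that measures this directly, and it is the one missing from the body of the protocol.

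The primary definition has a separate gap. It tests position and retrieval but not guidance. If the device stays where it was put but gives no signal, and the surgeon retrieves it with a second SCOUT or a wire, both conditions are met. The headline success rate would then include a surgery that the long-dwell device did not guide. In a single-arm pilot of 25 to 35 patients, one such case visibly changes the figure.

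**Working it through.** **Step 1. The two lists of secondary endpoints.** Days from placement to surgery, placement within 1 cm, migration of no more than 5 mm, and device-related complications appear in both. The number of additional localizations appears in the Summary only.

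**Step 2. Each rescue route followed through the endpoints.** Assume that the device was placed within 1 cm at the start and was removed at surgery.

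| Endpoint | Moved more than 5 mm, then rescued | Did not move, not detected, then rescued |
|---|---|---|
| Primary (4.1.1) | Failure: did not stay in place | Success: stayed in place and was removed |
| Placement within 1 cm (4.1.2) | Pass | Pass |
| Stability, 5 mm (4.1.2) | Fail | Pass |
| Complication rate (4.1.2) | Not determined by the text | Unclear, see below |
| Additional localizations (Summary only) | Counted | Counted |

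The stability row follows from Section 4.1.2: "The SCOUT should not migrate more than 5 mm between day 0 - 365 days pre-surgery". The complication row for a silent device is unclear because Section 8.1.5 contradicts itself. It names nonfunction among the potential unanticipated device effects, and it also says that device failures and malfunctions are not adverse events. Even if nonfunction entered the complication rate, the rescue procedure itself would not be counted there.

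The gap is therefore the right-hand column: non-detection without migration. Restoring the fifth endpoint would show that case but would not change its primary classification, which comes from the primary definition alone.

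**Step 3. How likely is a rescue?** The plan's own figure is 1/150 = 0.67%, which agrees with its statement of less than 1%. The exact 95% interval for 1/150 is 0.02% to 3.66%. The chance of at least one rescue among n patients is 1 − (1 − p)^n.

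- p = 1/150: 1 − (149/150)^25 = 15.4%; 1 − (149/150)^35 = 20.9%.
- p = 1%: 22.2% (n = 25) and 29.7% (n = 35).
- p = 3% (assumed, inside the interval above): 53.3% and 65.6%.

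**Step 4. What one rescue does to the success rate.** Assume one rescue for non-detection without migration and no other failure. Intervals are exact (Clopper–Pearson). When all n succeed, the lower limit is 0.025^(1/n). For x successes of n, the limits are the 0.025 quantile of Beta(x, n − x + 1) and the 0.975 quantile of Beta(x + 1, n − x).

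- n = 25, rescue credited: 25/25, lower limit 0.025^(1/25) = 86.3%.
- n = 25, not credited: 24/25 = 96.0% (79.6–99.9). Rescued: 1/25 = 4.0% (0.1–20.4, by complement).
- n = 35, rescue credited: 35/35, lower limit 0.025^(1/35) = 90.0%.
- n = 35, not credited: 34/35 = 97.1% (85.1–99.9). Rescued: 1/35 = 2.9% (0.1–14.9, by complement).

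One such case moves the point estimate by 4.0 or 2.9 points, and the lower limit by 86.3 − 79.6 = 6.7 or 90.0 − 85.1 = 4.9 points.

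**The case against.** The strongest reply is that this is a mismatch of lists in a descriptive pilot. The Summary belongs to the same protocol and keeps the endpoint. Section 9.2 refers to the endpoints without citing a section, so it can be read as including the fifth. That stands: a reader might infer that no endpoint shows a rescue, or that a rescue leaves no trace, and the documents support neither. Section 8.1.5 also has device deficiencies documented and reported to the sponsor.

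A reader might also infer that the missing item is what lets a rescued surgery count as a success. It is not. The primary definition does that, and would still do so with all five endpoints listed.

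Much of the rescue pathway is already covered: a device that moved is a primary failure and, beyond 5 mm, a stability failure. That stands and limits the point to unmoved, undetected devices.

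Finally, an extra localization need not mean that the first device failed. The surgeon decides whether to request one, and Sections 5.1 and 7.2 allow additional studies to change the surgical plan. That also stands, and it is why the reason for each additional localization matters.

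One could argue that successful removal implies removal under SCOUT guidance, given the objective. The definition does not say so, and two people classifying the same case could disagree.

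**Conclusion.** The point holds with a limited reach. There is an unresolved inconsistency: five secondary endpoints in the Summary, four in Section 4.1.2, and no rule on which list is analysed. Independently, the primary definition credits a device that did not move, could not be detected and was removed with help, so the success rate does not by itself show that the device guided the excision.

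The size is modest at the protocol's anticipated risk: about a 15% to 21% chance of any rescue, and 2.9 to 4.0 points on the success rate for each rescue of the hidden kind. Two assumptions matter. First, the 1/150 figure is not split between non-detection and migration, so the chance of a hidden rescue may be lower than the chance of any rescue. Second, the documents do not give the dwell time of those 150 patients, so the figure may not carry over to 31–365 days. The single rescue in the illustration is assumed.

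Sample size and procedures are unaffected. The correction is worth making because it is cheap and determines what the headline rate can support.

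**What to change.** 1. List the same five secondary endpoints in Section 4.1.2 as in the Summary.
2. Report the number of additional localizations. Also report the number and proportion of patients who needed one because the first device was not detected or not verified in position, with an exact 95% interval. Keep additional localizations made for other reasons, such as a changed surgical plan, separate.
3. Keep the primary endpoint as defined, and report beside it success without such an additional localization.
4. Reconcile the statements in Section 8.1.5 so that it is clear whether nonfunction enters the complication rate.
5. Confirm that the case report forms record each additional localization and its reason. The forms are not in the documents. Section 10 lists additional localization imaging among the images, but that does not show that the reason is captured.

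The cost is a few lines of text, one extra table row, possibly one field on a form, and a success figure that may be less favourable.

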2.1 Description of the SAVI SCOUT Breast Localization and Surgical Guidance System

The SAVI SCOUT Surgical Guidance System (SAVI SCOUT, Cianna Medical, Inc.) is an FDA cleared medical device that aids in the surgical excision of breast lesions without the use of wires or radioactive materials. The system employs nonradioactive light-activated radar SCOUT device, which is placed in breast or axillary lesions under imaging guidance up to 365 days prior to surgery, to guide the surgical excision of non-palpable lesions (Standard of Care).

The system consists of the SCOUT (device) and two major components:

1. A localization SCOUT (device) is placed, percutaneously via a 16-gauge needle at the breast/axillary lymph node lesion. The device uses light (radar) technology to activate an audio and numeric signal to aid the surgeon to locate the target tissue. The device contains nitinol wire, which is a standard medical material composed of nickel and titanium. After placement, the device is safe and visible under all standard imaging modalities (Mammogram, Ultrasound, CT, PET-CT, X-ray, and MRI).
2. A handpiece (PROBE) is used by the surgeon intra-operatively. In the operating room, the sterile PROBE is connected to the console and is placed in direct contact with the skin or within breast/axillary tissue to send /receive the audio and numeric signal to guide the surgeon.

Figure 1. SCOUT System Components

2.2 Rationale

The SAVI SCOUT (Cianna Medical, Inc.) surgical guidance system received 510(k) U.S. Food and Drug Administration (FDA) approval in August 2014 (1). FDA clearance for long-term use was approved in October 2017 (2). This system is currently used as standard of care since 2015 in the MHS operating rooms by experienced breast surgeons (over 600 MHS breast cancer patients and over 28,000 U.S. breast cancer patients as of September 2016) (3, 5). MHS standard of care practice, the device(s) is placed at the target lesion(s) under image-guidance by the radiologist up to 365 days prior to surgery.

Patients with certain types of breast cancer undergo neoadjuvant treatment with biologic (hormonal) and/or chemotherapy with the goal of decreasing the tumor volume prior to definitive surgery. If the original cancer lesion(s) resolve completely, this is called complete pathologic response (pCR) (4). pCR and even a partial response, while good for the patient, can result in disappearance or poor visualization of the target and often render pre-operative image-guided localization by the radiologist more difficult and less reliable. This can result in unintended larger, more disfiguring breast cancer surgery. Therefore, if the SCOUT device(s) can be placed prior to treatment response, when the lesion(s) is clearly visualized on imaging, accurate image-guided targeting is optimal and thus placement and subsequent surgery should be more accurate. If this pilot study demonstrates successful performance of the device without device-related complications, it will bring improved value to future patients who will require fewer and/or less extensive pre-operative and surgical procedures. Some value may also be provided to subjects as the targeting before tumor shrinkage is expected to be more accurate.

During the excisional procedure, the surgeon uses the console and PROBE to locate the SCOUT device(s) and breast and/or axillary tissue for targeted excision.

This pilot study will assess the performance of FDA cleared SCOUT system over a longer duration prior to breast and/or axillary lymph node surgery.

